10.4. Time to Best Overall Response

Time to unconfirmed BOR is derived for RECIST 1.1 and irRECIST separately. The Kaplan-Meier estimate of median time to BOR for both RECIST 1.1 and irRECIST along with a 2-sided 95% CI () will be provided in a table using Safety and EE Populations.

Time to the BOR is measured from first dose date to the earliest of unconfirmed BOR (or irBOR) (CR or PR) based on RECIST 1.1 (irRECIST respectively). A subject whose BOR has never reached the level of CR or PR will be censored on the date of his or her last adequate tumor assessment. Subjects without valid baseline or post baseline tumor assessments will be censored on the study discontinuation date. Any valid overall post-baseline tumor assessment (not missing or not recorded as “not done” or “not all evaluable”) are considered adequate tumor assessments in this case.

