CR	SD	SD provided minimum criteria for SD duration met, otherwise, PD
CR	PD	SD provided minimum criteria for SD duration met, otherwise, PD
CR	NE	SD provided minimum criteria for SD duration met, otherwise NE
PR	CR	PR
PR	PR	PR
PR	SD	SD
PR	PD	SD provided minimum criteria for SD duration met, otherwise, PD
PR	NE	SD provided minimum criteria for SD duration met, otherwise NE
NE	NE	NE

Abbreviations: CR = complete response, PR = partial response, SD = stable disease, PD = progressive disease, NE = non evaluable.

[1] If a CR is truly met at first time point, then any disease seen at a subsequent time point, even disease meeting PR criteria relative to baseline, makes the disease PD at that point (since disease must have reappeared after CR). Best response would depend on whether minimum duration for SD was met. However, sometimes 'CR' may be claimed when subsequent scans suggest small lesions were likely still present and in fact the subject had PR, not CR at the first time point. Under these circumstances, the original CR should be changed to PR and the best response is PR.

Note: All responses after first PD will not be considered as a response.

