10.5. Progression-Free Survival (PFS) and Time to Progression (TTP)

10.5.1. Progression-Free Survival (PFS)

PFS is defined as the time from the first dose date until tumor progression or death, whichever occurs first.

Based on Food and Drug Administration (FDA) Guidance () a subject who has neither progressed nor died or who progresses or dies after an extended lost-to-follow up time (two or more missed assessments) will be censored on the date of last adequate tumor assessment. Subjects without valid baseline or post-baseline tumor assessments will be censored on their first dose date (i.e. the first dose of CC-122 or Nivolumab whichever occurred first). Censoring rules are defined in [Table 8](#).

For PFS by irRECIST, the date of progression is the first date of PD as defined under irRECIST.

Analysis of PFS will be provided for RECIST and irRECIST separately and be presented for the Safety and EE Populations. Median of PFS times will be calculated using the Kaplan-Meier method and the corresponding 95% CIs will be presented. The number of events, subjects censored, and the Kaplan-Meier estimates of PFS rates at the time points of 3 months (90 days) and 6 months (180 days), along with standard errors of rate estimates (Greenwood’s formula,) will also be provided.

Table 8: Progression and Censoring Rules for PFS Analysis

Situation	Date of Progression or Censoring	Outcome
No baseline assessment	Date of first dose of study drug	Censored
No progression	Date of last visit with adequate assessment	Censored
Treatment discontinuation for toxicity or other reason without progression	Date of last visit with adequate assessment	Censored
New anticancer treatment started with no claim of progression	Date of last visit with adequate assessment	Censored
Death before first PD assessment	Date of death	Progressed
Death between adequate assessment visits or after patient misses one assessment visit	Date of death	Progressed
Death or progression after an extended lost-to-follow up time (two or more missed assessments)	Last visit with adequate assessment	Censored

In dose expansion phase, for the Safety and EE Populations, Kaplan-Meier survival curves of PFS will be presented for RECIST 1.1 and irRECIST separately; subgroup will be presented in the same figure using different lines colour/symbol.

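### SAP 10.4 censors RECIST 1.1 progressors and deaths in a Kaplan-Meier time to response as if they could still respond, so a median can be printed when fewer than half respond

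*SAP*

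**What the plan says.** SAP 10.4 promises "The Kaplan-Meier estimate of median time to BOR for both RECIST 1.1 and irRECIST along with a 2-sided 95% CI", in a table, for the Safety and EE Populations. The clock starts at first dose and the event is the earliest unconfirmed CR or PR. The rule for non-responders begins "A subject whose BOR has never reached the level of CR or PR will be censored" and fixes the date: such a subject "will be censored on the date of his or her last adequate tumor assessment". Progression and death get no separate treatment.

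Two other parts of the SAP close the RECIST 1.1 response window at progression. The note to Table 5 in 10.1 reads "All responses after first PD will not be considered as a response", and 10.2 derives BOR only up to the date of progression or data cut-off. For irRECIST, 10.2 takes irBOR over all post-baseline time points and states no stop at irPD.

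For unscanned subjects 10.4 says: "Subjects without valid baseline or post baseline tumor assessments will be censored on the study discontinuation date". For PFS, 10.5.1 says such subjects "will be censored on their first dose date", and TTP in 10.5.2 follows the same convention.

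SAP 10.3 limits Kaplan-Meier estimates of DoR and duration of SD to groups with at least three qualifying subjects. SAP 10.4 has no such limit.

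**The concern.** Kaplan-Meier treats a censored subject as having the same future chance of the event as those still at risk. A RECIST 1.1 progressor has none. Censoring that subject passes the probability to the few who remain, so each later response counts for too much. A median read from this estimate can look like the time by which half the subjects responded when far fewer did.

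The dose cohorts are where this is most likely to show. SAP section 10 presents efficacy by dose cohort, and protocol 7.8 sets cohorts at about three to six evaluable subjects. Expansion was cancelled (SAP section 15, item 2), so there is no larger group to steady the estimate.

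The rule for unscanned subjects is a second, smaller matter. No response can be observed in them, yet they stay in the risk set until they leave the study, so the estimate depends on an administrative date.

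**Working it through.** SAP 10.4 states no figure to reproduce, so the check applies its rules to illustrative data.

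**Inputs from the documents**
- Scans at weeks 8, 16, 24, 32 and 40, then every 12 weeks (SAP section 10).
- Response rates of 20% and 35%, and up to about 20 escalation subjects (protocol 9.3).
- Survival follow-up to 2 years, or 104 weeks (protocol 6.4.3).

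**Inputs assumed:** all response and progression times, the share never scanned, and when those subjects discontinue.

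**Estimators.** S(t) is the product over response times of (1 − responses/at risk), and the SAP's implied response probability is 1 − S. The comparator is cumulative incidence, in which progressors and unscanned subjects stay in the denominator as non-responders.

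**1. One cohort of six.** Three progress at week 8, two at week 16, and one responds at week 24. At week 24 one subject is at risk and has the event, so S = 1 − 1/1 = 0. The table shows a median of 24 weeks. The response proportion is 1/6 = 17%.

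**2. Twenty subjects, all scanned**

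| Week | 4 responders: responses / at risk | S | 7 responders: responses / at risk | S |
|---|---|---|---|---|
| 8 | 2/20 | 0.900 | 3/20 | 0.850 |
| 16 | 1/10 | 0.810 | 2/11 | 0.695 |
| 24 | 1/5 | 0.648 | 1/6 | 0.580 |
| 32 | none | 0.648 | 1/2 | 0.290 |

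Progressions at weeks 8, 16, 24 and 52 number 8, 4, 3 and 1 in the first example, and 6, 3, 3 and 1 in the second. The first gives 1 − S = 0.352 against 4/20 = 0.20, with no median. The second gives 0.710 against 7/20 = 0.35, with a median of 32 weeks although 13 of 20 never responded.

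**3. Expected size at a true 20%.** Assume responses of 10%, 6% and 4% of subjects at weeks 8, 16 and 24, and exponential progression in the other 80%. With a progression median of 8 weeks, half the remaining non-responders leave at each scan. The at-risk fractions are then 1.00, 0.50 and 0.24, and S = 0.90 × (1 − 0.06/0.50) × (1 − 0.04/0.24) = 0.66. So 1 − S = 34% at week 24. Medians of 13 and 17 weeks give 27% and 25%.

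**4. How often a median is printed (simulation)**
- n=20, timing as in step 3: 17%, 5% and 2% of trials for progression medians of 8, 13 and 17 weeks.
- n=6, same timing: 28%, 19% and 17% of cohorts. In 18%, 9% and 6% of cohorts at most two of six responded.
- n=20, assuming instead a 40% chance at each scan of either response or progression: 39% of runs at a true 20% and 74% at a true 35%. Cumulative incidence gives about 0% and 12%.

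**5. Unscanned subjects.** Take the seven-responder example with four subjects never scanned, leaving progressions of 4, 2, 2 and 1.
- Discontinuation at week 104: S = 17/20 × 11/13 × 8/9 × 5/6 = 0.533, so 1 − S = 0.467 and there is no median.
- Discontinuation at week 26: the week-32 factor becomes 1/2, so 1 − S = 0.680 and the median is 32 weeks.
- Censored at first dose: S = 13/16 × 7/9 × 4/5 × 1/2 = 0.253, so 1 − S = 0.747 and the median is 32 weeks.

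The same responses therefore give different tabulated results, depending only on when four unobserved subjects left. Simulation with the step 4 assumption of 40% per scan, a true 20% and 20% unscanned gives 0.46 (week 26), 0.31 (week 104) and 0.51 to 0.53 (first dose), against about 0.20 for cumulative incidence.

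**The case against.** The strongest reply is that little depends on this endpoint. Time to best response is not in the readable part of the endpoint table or in protocol 9.6, all analyses are descriptive, and no rule uses the median. ORR is reported with exact intervals, and individual times to BOR are listed. SAP section 15 also drops exploratory efficacy analyses limited by the data. All of this stands and limits the severity. But section 15 does not name this analysis, so 10.4 remains in force.

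Four stronger readings are tempting, and the documents do not support them.
- **That the post-progression argument holds equally for irRECIST.** The no-response-after-PD rule sits under a RECIST 1.1 table, and irBOR runs over all time points. For irRECIST the objection applies mainly to death and end of scanning.
- **That any printed median is an artefact.** In a cohort of six with a true rate of 20%, three or more respond with probability 1 − (0.262 + 0.393 + 0.246) = 10%. At 35% the figure is 35%. Some medians would be genuine.
- **That the unscanned rule adds to the bias.** It works against it. It also cannot touch the EE Population, which requires a baseline and a post-baseline assessment. The contrast with PFS is not complete either, because Table 8 counts a death before the first PD assessment as an event.
- **That a biased curve or landmark rate would be published.** SAP 10.4 promises only a tabulated median with its interval. The week-24 figures in the working show how far the underlying estimate moves; they are not a planned output.

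**Conclusion.** The point holds for RECIST 1.1. Censoring progressors and deaths here is informative, and 1 − S exceeds the response proportion whenever a response follows another subject's censored progression. That direction follows from the SAP's own rules. The size does not: at a true 20% response rate and n=20, the chance of printing a median ran from 2% to 39% across the assumed timings. In cohorts of three to six a single late responder can produce one, and 10.4 lacks the minimum-number condition used in 10.3.

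The unscanned rule is an unexplained inconsistency confined to the Safety Population. It pulls the estimate down and ties it to the discontinuation date. In every scenario run, the net estimate still exceeded the true response proportion.

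The impact is minor, but the correction is cheap and worth making.

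**What to change.** In SAP 10.4, replace the Kaplan-Meier median with a summary among responders only: n, median and range of time to first CR or PR, for each criterion and population.

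If an all-subject estimate is wanted, use cumulative incidence of response. Take PD and death as competing events for RECIST 1.1 and death for irRECIST, with the handling of end of scanning stated. Keep subjects without valid scans in the denominator as non-responders, and state that rule once.

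Do not keep Kaplan-Meier and merely move unscanned subjects to first-dose censoring. That would align 10.4 with PFS and TTP but increase the upward bias (0.467 to 0.747 in the week-104 example).

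The cost is one changed table and a short text edit. No new data are needed, and the responders-only summary takes less programming than the present plan.

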10.5. Progression-Free Survival (PFS) and Time to Progression (TTP)

10.5.1. Progression-Free Survival (PFS)

PFS is defined as the time from the first dose date until tumor progression or death, whichever occurs first.

Based on Food and Drug Administration (FDA) Guidance () a subject who has neither progressed nor died or who progresses or dies after an extended lost-to-follow up time (two or more missed assessments) will be censored on the date of last adequate tumor assessment. Subjects without valid baseline or post-baseline tumor assessments will be censored on their first dose date (i.e. the first dose of CC-122 or Nivolumab whichever occurred first). Censoring rules are defined in [Table 8](#).

For PFS by irRECIST, the date of progression is the first date of PD as defined under irRECIST.

Analysis of PFS will be provided for RECIST and irRECIST separately and be presented for the Safety and EE Populations. Median of PFS times will be calculated using the Kaplan-Meier method and the corresponding 95% CIs will be presented. The number of events, subjects censored, and the Kaplan-Meier estimates of PFS rates at the time points of 3 months (90 days) and 6 months (180 days), along with standard errors of rate estimates (Greenwood’s formula,) will also be provided.

Table 8: Progression and Censoring Rules for PFS Analysis

Situation	Date of Progression or Censoring	Outcome
No baseline assessment	Date of first dose of study drug	Censored
No progression	Date of last visit with adequate assessment	Censored
Treatment discontinuation for toxicity or other reason without progression	Date of last visit with adequate assessment	Censored
New anticancer treatment started with no claim of progression	Date of last visit with adequate assessment	Censored
Death before first PD assessment	Date of death	Progressed
Death between adequate assessment visits or after patient misses one assessment visit	Date of death	Progressed
Death or progression after an extended lost-to-follow up time (two or more missed assessments)	Last visit with adequate assessment	Censored

In dose expansion phase, for the Safety and EE Populations, Kaplan-Meier survival curves of PFS will be presented for RECIST 1.1 and irRECIST separately; subgroup will be presented in the same figure using different lines colour/symbol.

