7.8. Criteria for Dose Escalation

The SRC will make dose escalation decisions. The decision criteria for dose escalation are:

- If no DLT is observed in the first 3 evaluable subjects during the first cycle, dose escalation to the next higher dose level may occur.
- If 1 out of 6 evaluable subjects experiences DLT during the first cycle, dose escalation to the next higher dose level may occur. Additional subjects will be enrolled to expand the cohort to 6 evaluable subjects if less than 6 subjects are evaluable when the DLT is observed.
- If 2 or more out of up to 6 evaluable subjects experience a DLT during the DLT assessment period in a cohort, any further recruitment into that cohort will cease and this dose will be defined as an NTD.
- The SRC will determine if additional subjects will be enrolled in a parallel or at lower dose cohorts to have 6 evaluable subjects in order to define RP2D, or whether an intermediate dose level or an intermittent dosing schedule will be explored in up to 6 newly enrolled subjects. Additional subjects may be added at a given dose level to further assess the safety and/or PK.

Based on above criteria, if no DLT is observed in at least 3 evaluable subjects, the SRC may decide to escalate the dose to the next cohort.

If one DLT occurs prior to a decision by the SRC to dose escalate, the cohort will be expanded to enroll 6 evaluable subjects in total. Subjects 4 to 6 may be enrolled concurrently with the first 3 subjects if complete 28-day toxicity data are not yet available for the first 3 subjects.

If 1 subject out of 6 evaluable subjects experiences a DLT, the dose will be escalated in the next cohort, unless there are other safety considerations by the SRC. The dose may also be declared the RP2D.

The number of cohorts depends on incidence of DLT. A subject may experience more than 1 DLT. Dose escalation decisions are based on the number of subjects experiencing DLT events.

Intra-subject dose escalation beyond the dose initially assigned to a subject is not permitted in Cycle 1. Those continuing to take IP beyond Cycle 1, following approval by the SRC, may have the dose level increased providing the alternative dose level has been shown to be well tolerated by at least one cohort of other subjects in this study.

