9.6. Efficacy Analysis

Efficacy analyses will be based on the Treated Population and certain efficacy analyses will also be performed on the EE Population.

The efficacy variables include ORR, DCR, duration of response (DoR), PFS, TTP and OS. Tumor response and progression will be determined by the Investigator based on RECIST 1.1 ([Eisenhauer, 2009](#)) as a primary guideline, and irRECIST ([Bohnsack, 2014](#)) as an exploratory assessment.

Tumor response will be summarized using frequency tabulation. Two-sided 95% Clopper-Pearson exact CIs of the response rate will be provided ([Clopper, 1934](#)). A case-by-case description of all subjects who exhibited a complete or partial response will be provided.

The Kaplan-Meier estimate of the median of PFS, OS, DoR and TTP along with their 95% CI will be provided as appropriate ([Brookmeyer, 1982](#)). Progression free survival and OS rates at

selected time point(s) will be computed using the Kaplan-Meier estimates, along with standard errors of rate ([REDACTED]).

Other exploratory efficacy variables, such as AFP reduction, etc, will be summarized using frequency tabulations for categorical variables and/or descriptive statistics for continuous variables, as appropriate. Alpha-fetoprotein response rate will be provided with its 95% CI. Alpha-fetoprotein response is defined as normalization or > 50% decline from baseline. The AFP response rate is the percentage of subjects with baseline elevation in AFP who meet AFP response criteria. A descriptive analysis for other evidence of antitumor activity will be provided based on clinical, radiographic, and biologic assessments of efficacy.

Listings and graphical displays will be provided where useful for the interpretation of results.

Full details on the efficacy analysis are described in the SAP.

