10. EFFICACY ANALYSIS

The efficacy endpoints of this study include ORR, DCR, DoR, PFS, TTP and OS. Tumor response and progression will be determined by the Investigator based on RECIST 1.1 () as a primary guideline, and irRECIST () as an exploratory assessment.

Tumor assessments will be performed at screening (up to 28 days before the Cycle 1 Day 1 [C1D1] dose), every 8 weeks (\pm 7 days) for the first 5 evaluations (10 months) and thereafter every 12 weeks (\pm 7 days), regardless of treatment status. Tumor assessments should also be performed at any time, if clinically indicated. Tumor assessments should continue at the defined schedule until radiologic disease progression or new anticancer therapy, beyond the end of treatment if necessary.

Following disease progression, survival status will be determined approximately every 3 months thereafter until 2 years from enrollment, lost to follow-up, death or withdrawal of consent, whichever occurs sooner.

Survival follow-up may be conducted by record review (including public records) and/or telephone contact with the subject, family, or the subject's treating physician.

All summaries, analyses and figures of efficacy data will be presented as applicable by dose cohorts in dose escalation part, by selected subgroups in dose expansion part, by selected subgroup at the expanded dose with subjects from both parts, unless otherwise specified.

Individual listings of tumor assessment and derived endpoints will be provided, which include:

- For RECIST 1.1 and irRECIST, listing for total measured tumor burden (TMTB), including change (in mm and percentage) from baseline and change from nadir for each visit; the TMTB is calculated separately for target and new measurable lesions as the sums of the respective diameters of target and new measurable lesions; nadir is the smallest TMTB of all assessments since study treatment starts before the current assessment.
- Listing for non-target lesions (RECIST 1.1) and new non-measurable lesions (irRECIST);
- Listing of overall response by visit unconfirmed and confirmed best overall response (BOR) using RECIST 1.1;
- Listing of unconfirmed BOR using irRECIST;
- Listing of DoR, duration of Stable Disease (SD) and time to BOR (using RECIST 1.1);
- Listing of PFS, TTP (using RECIST 1.1) and OS with flags for the censored data;
- Listing of DoR, duration of Stable Disease (SD) and time to BOR (using irRECIST);

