15. CHANGES TO THE STATISTICAL ANALYSES SECTION OF THE PROTOCOL

1. The protocol defines “enrolled population” as “All subjects who meet all the inclusion/exclusion criterion and are eligible for the study.” As written, this definition excludes those subjects who were enrolled into the study and later discovered to have not met an inclusion/ or met an exclusion criteria. In order to accurately reflect ALL subjects who were enrolled into the study, the definition of enrolled population is expanded to remove the inclusion/exclusion criteria caveat which include all subjects who were assigned an enrollment number. The enrolled subjects who did not meet inclusion/exclusion criteria will be captured as protocol violators, which will be reported separately in a listing of protocol violations.
2. Per study HODC (Hematology and Oncology Development Committee) decision, this study will not be moving into expansion phase, thus the analyses described in the protocol for expansion phase as well as the exploratory efficacy analyses limited by the data will not be performed.
3. The following exploratory objectives, originally described in the study protocol, are not considered in this SAP and will be described in separate reports, if applicable.
 - To determine the relationship between baseline gene expression profiling, deoxyribonucleic acid (DNA) mutations, T cell clonality and protein biomarker expression with clinical endpoints including tumor response, response duration and progression free survival (PFS)
 - To determine the relationship of CC-122 and Nivolumab pharmacodynamics (PD) biomarkers in peripheral blood and changes in immune markers in tumor to clinical endpoints including tumor response, response duration and PFS
 - To determine the relationship between the plasma concentrations of CC-122 and Nivolumab and [REDACTED]s, safety, and clinical endpointsTherefore, the corresponding analyses including the analysis [REDACTED] described in Section 9.9 of the protocol are not considered in this SAP.

4. Futility analysis is no longer planned in this study.
5. Shift tables for vital signs and LVRF are no longer needed in this study.

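### Cohort-level PFS rates carry only a Greenwood standard error, which is 0 for any cohort with no progression or death by the time point

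*SAP*

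**What the plan says.** SAP 10.5.1 treats the median and the rates differently. For the median: "Median of PFS times will be calculated using the Kaplan-Meier method and the corresponding 95% CIs will be presented". For the time points it lists "The number of events, subjects censored, and the Kaplan-Meier estimates of PFS rates", and specifies the rates as "PFS rates at the time points of 3 months (90 days) and 6 months (180 days), along with standard errors of rate estimates", by Greenwood's formula. It specifies no confidence interval and no number at risk for those rates. Protocol 9.6 is the same: rates at selected time points "will be computed using the Kaplan-Meier estimates, along with standard errors of rate", with no interval. SAP 5.1.1 mentions 95% CI limits only to set decimal places.

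The reporting level is set in SAP 10: "All summaries, analyses and figures of efficacy data will be presented as applicable by dose cohorts in dose escalation part". SAP 15, item 2, records that "this study will not be moving into expansion phase", so the escalation cohorts are what remains. Their usual size follows from Protocol 7.8: "If no DLT is observed in the first 3 evaluable subjects during the first cycle, dose escalation to the next higher dose level may occur". A single DLT expands the cohort to six evaluable subjects, and up to six may be enrolled concurrently (Protocol 3.1). Further subjects may be added, so 3 to 6 is the usual range and not a ceiling.

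For response and disease control rates in the same cohorts, SAP 10.2 plans exact Clopper-Pearson 95% intervals.

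**The concern.** A standard error is printed beside a rate to show how far the rate can be trusted. Greenwood's estimate depends on the events observed. Where there are none it is 0, because the sum it is built from is empty, and this says nothing about how well the rate is known. In a cohort of three with no event, the table would show 100% with SE 0. In that cohort the median PFS and its CI cannot be estimated either, so the zero is the only numerical precision left for PFS. It errs towards certainty. At stake is how a reader weighs PFS in a small dose-finding report; no formal conclusion depends on it.

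**Working it through.** **Inputs.** Time points of 90 and 180 days and Greenwood's formula (SAP 10.5.1); reporting by dose cohort (SAP 5.1.1 and 10); cohorts of about 3 to 6 (Protocol 3.1 and 7.8). The documents state no PFS rate, SE or interval, so there is no planned figure to reproduce. The true PFS rate at a time point is therefore an assumption, varied here from 50% to 80%.

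**Step 1: the formula.** SE(t) = S(t) × √( Σ dᵢ / [nᵢ(nᵢ − dᵢ)] ), summed over event times up to t. Without censoring this equals √(S(1 − S)/n).
- No event by t: the sum is empty and S = 1, so SE = 0 for any n.
- Everyone has an event by t: S = 0 and the last term divides by zero, so the formula reads 0 × ∞. The uncensored form gives a limit of 0; software may print 0 or a missing value.

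**Step 2: what the SE hides (no censoring before t).** Exact (Clopper-Pearson) limits at the boundary are 0.025^(1/n) to 1 when all are event-free, and 0 to 1 − 0.025^(1/n) when none is. For example, 0.025^(1/3) = 0.292 and 0.025^(1/6) = 0.541.

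| n | Event-free | Greenwood SE | Exact 95% limits |
|---|---|---|---|
| 3 | 3 (100%) | 0 | 29% to 100% |
| 3 | 2 (67%) | 0.272 | 9% to 99% |
| 3 | 0 (0%) | 0 as a limit | 0% to 71% |
| 6 | 6 (100%) | 0 | 54% to 100% |
| 6 | 5 (83%) | 0.152 | 36% to 99.6% |
| 6 | 3 (50%) | 0.204 | 12% to 88% |
| 6 | 0 (0%) | 0 as a limit | 0% to 46% |

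Between 5/6 and 6/6 the SE falls from 0.152 to 0, while the width of the exact interval falls only from 0.996 − 0.359 = 0.637 to 1 − 0.541 = 0.459.

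**Step 3: how often.** Without censoring, the chance that a cohort lands on 0% or 100% is pⁿ + (1 − p)ⁿ.

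| Assumed true rate p | n = 3 | n = 6 |
|---|---|---|
| 50% | 0.125 + 0.125 = 25% | 0.0156 + 0.0156 = 3% |
| 60% | 0.216 + 0.064 = 28% | 0.0467 + 0.0041 = 5% |
| 70% | 0.343 + 0.027 = 37% | 0.1176 + 0.0007 = 12% |
| 80% | 0.512 + 0.008 = 52% | 0.2621 + 0.0001 = 26% |

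The formula is symmetric, so true rates of 20% to 50% give the same chances. For three independent cohorts with a common rate, the chance that at least one is at a boundary at a given time point is:
- sizes 3, 3 and 6: 1 − 0.75² × 0.969 = 46% at p = 50%, and 1 − 0.63² × 0.882 = 65% at p = 70%;
- sizes 6, 6 and 6: 1 − 0.969³ = 9% at p = 50%, and 1 − 0.882³ = 31% at p = 70%.

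**Step 4: censoring.** Scans are every 8 weeks at first (SAP 10), and a subject without progression is censored at the last adequate assessment (SAP 10.5.1, Table 8). Someone who leaves after the first scan is censored near day 56, before day 90. With no event the SE stays 0 however few remain. If one subject is still at risk at day 90, an exact limit on that subject alone runs from 0.025^(1/1) = 2.5% to 100%. The planned output would still be 100%, SE 0.

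**The case against.** The strongest case against acting is that nothing depends on this figure. PFS is secondary (SAP Table 2), the protocol summary calls all analyses descriptive, no PFS test or decision rule exists, and dose decisions rest on DLTs and committee review. SAP 10.5.1 also reports the numbers of events and of censored subjects, and SAP 10 adds subject listings with censoring flags. A careful reader can see that a cohort is small and has no events. All of this stands and limits the impact. It does not make the printed SE a correct measure of precision.

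A reader might infer more than the documents support:
- That planned 95% intervals for the rates would under-cover. The SAP plans no interval of the form estimate ± 1.96 SE; it plans an SE.
- That dose levels will be wrongly compared on PFS. No such comparison is planned.
- That cohorts at 0% or 100% are the least informative. This fits only in that the smallest cohorts reach a boundary most often. At a fixed n, a boundary result has the narrowest exact interval: width 0.459 for 6/6 against 0.882 − 0.118 = 0.764 for 3/6.
- That the minimum number required for duration of response and of stable disease (SAP 10.3) would cure the problem if extended to PFS. That minimum is three subjects, and a 3/3 cohort meets it.
- That SAP 15, item 2, removes the issue by dropping exploratory efficacy analyses limited by the data. PFS by RECIST 1.1 is a secondary endpoint and remains specified in SAP 10.5.1.

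**Conclusion.** The point holds as a limited reporting defect. The only precision measure planned for the cohort-level PFS rates is 0 in every cohort without a progression or death by the time point, and 0 as a limit or not computable when all subjects have had an event. For 3/3 and 6/6 the exact 95% limits are 29% to 100% and 54% to 100%. The result is not rare in cohorts of three (25% to 52%) and less common in cohorts of six (3% to 26%). Those chances rest on assumed true rates of 50% to 80% and on no censoring before the time point. That the SE is 0 when there are no events needs neither assumption and holds at any cohort size. No decision in the trial changes; what improves is the honesty of a descriptive table, at little cost.

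**What to change.** Keep the standard errors, because Protocol 9.6 names them and removing them would depart from it. Add to SAP 10.5.1, for each PFS rate at days 90 and 180, the number at risk and a two-sided 95% CI, with these rules:
- Estimate strictly between 0 and 1: complementary log-log interval.
- Estimate at 0 or 1, nobody censored before the time point: exact Clopper-Pearson interval, already the SAP's method for response rates.
- Estimate at 0 or 1 with earlier censoring: beta-product interval. At 100%, Clopper-Pearson on the number at risk is a conservative alternative.
- Follow-up ended without the curve reaching 0, and nobody remains at risk at the time point: report the rate as not estimable.

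The cost is one short SAP paragraph and slightly more programming, with no new data. The intervals will be visibly wide, as they should be for cohorts of this size.
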